6.1.5 Open-Label Phase

Subjects will receive their first dose of OL AZM in the clinic and study drug will be dispensed at Week 8/Visit 9 after the final trough vital sign measures of the Withdrawal Phase are recorded. Each subject will also be provided with a home blood pressure monitoring (HBPM) device and a BP diary so that daily BP measures can be recorded and reviewed by the investigator during the OL Phase (see [Section 9.1.16](#)).

Instructions for drug administration during the OL Phase will be the same as during the double-blind (DB) phases; ie, study medication will be administered orally with water, at an agreed upon (by the site and subject) consistent time of day, with or without food, and will be administered in the clinic on days when a visit is scheduled.

[figure not shown]
Throughout the OL Phase, subjects will be treated to achieve and maintain a target BP of <90th percentile for age, gender, and height. For subjects with CKD, a lower BP target may be utilized at the investigator's discretion. Evidence suggesting lower BP targets are appropriate and improve renal outcomes in this patient population is summarized in [Section 6.2.6](#).

All subjects will start the OL Phase receiving AZM 10 mg which can be titrated to higher dose(s) (up to 40 mg for subjects <50 kg or up to 80 mg for subjects \geq 50 kg), and additional antihypertensive medications can be added if needed to achieve target BP. If add-on therapy is needed, the type of medication added (eg a calcium channel blocker, such as amlodipine, a diuretic, such as hydrochlorothiazide, or a beta-blocker such as metoprolol) will be determined per the investigator's clinical judgment. The recommended treatment algorithm for the OL Phase is provided in [Figure 6.b](#).

In the event that down-titration or temporary or permanent discontinuation of antihypertensive medication is indicated, dose reduction or discontinuation should begin with the additional antihypertensive drug(s) first, before the dose of AZM is reduced or discontinued. During the OL Phase subjects may continue participation in the study if AZM is temporarily discontinued for less than 2 weeks. Treatment with a dose of AZM that is above the highest dose allowed for the body weight category (ie, to 80 mg in a subject <50 kg) is not allowed.

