- (h) Includes sitting and standing BP and pulse. Obtain a second set of 3 seated measurements if any of the initial BP readings differ by >8 mm Hg for SBP or >5 mm Hg for DBP; if clinic BP at any visit exceeds the 99th percentile for age, gender, and height by 15 mm Hg for SBP or 10 mm Hg for DBP, a repeat measurement should be obtained within 48 hrs and the subject withdrawn if BP remains elevated.
- (i) In the OL Phase, if BP is above the target (ie, seDBP and/or seSBP are not <90 th percentile for age, gender, and height), titrate study medication or add additional medication according to the recommended treatment algorithm provided in [Figure 6.b](#). A lower BP target may be employed for subjects with CKD at the investigator's discretion.
- (j) Previous medical history documentation is acceptable if assessment was performed within the previous 6 months.
- (k) Spontaneous reports of PTEs should be collected from the time that informed consent is acquired until the first dose of study drug.
- (l) Spontaneous reports of AEs and SAEs should be collected from the time of the first dose of study drug through 14 and 30 days, respectively, after the last dose.
- (m) Includes the following listed in [Table 9.a](#)- hematology, urinalysis and all serum chemistry except for HgA1c; fasting is not required.
- (n) Renal subpanel only; the renal subpanel may also be requested by the investigator at unscheduled visits after study drug is titrated.
- (o) For diabetic subjects only
- (p) One PK sample will be obtained 1 to 2 hrs post-dose on D1/V4. At W4/V6, 1 sample will be collected at trough (ie, 24 to 36 hours after the previous dose) and 1 at 3 to 5 hrs post-dose. At W6/V8, a sample will be obtained at trough.
- (q) Only female subjects \geq 12 years old and younger girls deemed by the investigator to be of reproductive potential.
- (r) Includes serum and urine pregnancy test at Screening and urine pregnancy test at all other visits.
- (s) Required only for subjects \geq 12 years old; may be performed for younger children if deemed appropriate by the investigator. Results must be negative for the subject to continue in the study.
- (t) The Week 6 ABPM should be completed only for subjects with a baseline ABPM that met quality criteria. The Week 52 ABPM is optional for subjects with a baseline ABPM that met quality criteria; participating subjects should return to the clinic \approx 24 hours after the fitting for device removal.

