For the 44-week, OL extension phase descriptive statistics will be presented on subjects overall (ie, all subjects) and by status of additional antihypertensive use for the endpoints collected during the extension phase as follows: (a) Change from Baseline at each study visit and at the Final/End-of-Study Visit in trough clinic seSBP, seDBP, and MAP and (b) The number and percent of subjects achieving target BP at the end of the 44-week open-label extension period. Baseline for the OL Phase will be the last value prior to the first dose of study drug in the DB Phase.

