6. GENERAL CONSIDERATIONS

The FAS will be the primary data set used for efficacy analyses of the DB Phase and the Withdrawal Phase, unless otherwise specified. Efficacy analysis (FAS, PPS) will use planned treatment and Safety Analysis will use actual treatment. All routine safety analysis will be based on the SAF. All analysis of data (i.e., efficacy and safety) from the OL Phase will use the SAF and subjects will be summarized overall (i.e., all subjects together) and by status of additional antihypertensive use (i.e., AZM alone versus AZM plus additional antihypertensives).

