9. DISPOSITION AND WITHDRAWALS

All subjects who provide informed consent will be accounted for in this study.

The number and percentage of subjects in each disposition category will be presented; there will be no inferential analysis of subject disposition data.

Disposition of all enrolled but not randomized subjects will be tabulated according to screen failure/run-in failure, including primary reason for screen/run-in failure (pretreatment event, major protocol deviation, lost to follow-up, voluntary withdrawal, study termination, did not meet entrance criteria, other) as entered on the electronic case report form (eCRF).

Disposition of all randomized subjects will be tabulated by study phase, treatment group, pooled AZM (for DB and Withdrawal phases only) and overall. Treatments for DB phase are Losartan, AZM low dose, AZM intermediate dose, AZM high dose. Treatments for Withdrawal phase are Placebo, Losartan, AZM low dose, AZM intermediate dose, AZM high dose. Treatments for OL phase are AZM alone, AZM plus additional antihypertensive.

Primary reasons for discontinuation of study drug/visits, as entered on the eCRF, will be tabulated by phase and treatment group; the reasons include adverse event, major protocol deviation, lost to follow-up, voluntary withdrawal, study termination, pregnancy, lack of efficacy, PI discretion and other.

Major protocol deviations will be summarized for RND by phase, treatment group, pooled AZM (for DB and Withdrawal phases only) and overall. Protocol deviations will be presented in a data listing. Also, violation of Inclusion/Exclusion criteria will be listed for RND.

The number of subjects included in each analysis population will be summarized by phase, treatment group, pooled AZM (for DB and Withdrawal phases only) and overall.

Subject disposition, study discontinuation and study visit dates and times will be listed based on RND.

Document: 2014-000674-18 Statistical Analysis Plan Version 7.0 Version Number: 7.0

Version Date:

13JAN2020

Township No. 00 TB B0040 Building 5

Template No.: CS_TP_BS016 Revision 5 Reference: CS_WI_BS005

Effective Date: 01Apr2018

Author:

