16. SAFETY OUTCOMES

All outputs for safety outcomes will be based on the Safety Analysis Set.

There will be no statistical comparisons between the treatment groups for safety data, unless otherwise specified with the relevant section.

Safety analyses will be presented separately for the different study phases (i.e., DB, Withdrawal, and OL Phases). Summaries for the DB and Withdrawal Phases will be by Overall (i.e., all subjects), AZM treated subjects (pooled), and by the individual treatments; summaries for the OL Phase will by Overall and by status of additional antihypertensive use (i.e., AZM alone and AZM plus additional antihypertensive).

For safety analysis, baseline value for the DB Phase analyses will be the last available value prior to the first dose of DB Phase study drug. Baseline value for the Withdrawal Phase will be the last available value from the DB Phase. Baseline value for the OL Phase will be the last available value prior to the first dose of DB Phase study drug.

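### Open-label results are split by add-on status, which follows the child's BP response to AZM and has no dating rule, so the AZM-alone column is response-selected and event assignment is undefined

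*SAP*

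**What the plan says.** Protocol 6.1.5 puts every child on AZM at OL entry: "All subjects will start the OL Phase receiving AZM 10 mg which can be titrated to higher dose(s". In the same section, "additional antihypertensive medications can be added if needed to achieve target BP". The vital-signs footnote to the schedule in Protocol 9.3 gives the trigger. When BP is above target, the site is to "titrate study medication or add additional medication according to the recommended treatment algorithm".

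The reporting groups follow from that treatment path. SAP section 6 says that "subjects will be summarized overall (i.e., all subjects together" and also "by status of additional antihypertensive use (i.e., AZM alone versus AZM plus additional antihypertensives". Protocol 13.1.3 applies the split to BP change and target attainment, "by status of additional antihypertensive use for the endpoints collected during the extension phase". SAP section 16 does the same for safety, "by status of additional antihypertensive use (i.e., AZM alone and AZM plus additional antihypertensive".

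SAP section 9 treats the two statuses as treatment groups: "Treatments for OL phase are AZM alone, AZM plus additional antihypertensive". SAP Appendix 1 lists them as the OL output columns. SAP section 10 tabulates baseline characteristics by treatment group, with p-values, for each phase including OL.

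**The concern.** The split is made on something that happens after OL entry and is driven largely by the outcome being reported. A child whose BP stays above target on AZM is a candidate for an add-on and so for the other column. The AZM-alone column tends to lose its failures, and its target rate and mean BP fall are then computed mainly among children in whom AZM was enough. Nothing in the SAP warns the reader of this.

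The status also changes over time, and neither document says whether it is taken as ever/never, at the visit, at event onset or at the Final Visit. For adverse events this decides which column an early event falls in.

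Safety and tolerability of AZM in the OL phase is part of a secondary objective (Protocol 5.1.2). Protocol 4.2 adds long-term efficacy. OL BP outcomes are additional endpoints (Protocol 5.2.4).

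**Working it through.** The plan states no add-on rate, target rate or event rate for OL, so there is no figure to reproduce. The 44-week OL length and the recommended four weeks or so per dose level come from the protocol. All other inputs below are assumptions.

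**1. Selection in the AZM-alone target rate.** Let p be the proportion AZM would control if nobody received an add-on, and a the proportion of uncontrolled children who receive one. Assume controlled children receive none and nobody leaves. The column then shows D = p / (p + (1 − p)(1 − a)).

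| p | a | D |
|---|---|---|
| 0.60 | 0 | 0.60/1.00 = 60% |
| 0.60 | 0.50 | 0.60/0.80 = 75% |
| 0.60 | 0.80 | 0.60/0.68 = 88% |
| 0.60 | 0.90 | 0.60/0.64 = 94% |
| 0.60 | 1.00 | 0.60/0.60 = 100% |
| 0.40 | 0.80 | 0.40/0.52 = 77% |
| 0.70 | 0.80 | 0.70/0.76 = 92% |

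The closer sites keep to the algorithm, the less D says about p.

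**2. Is there one column per child?** The wording of the plan points that way:
- Disposition and baseline tables need one group per child, and SAP 9 and 10 use these statuses as OL groups.
- SAP 5.4 analyses each child by the medication received in the phase being summarised.
- SAP 16.1 bounds OL treatment-emergent events by the first and last OL dose only. The add-on date plays no part.
- The same section does have a switch rule for the Withdrawal Phase: events in the first 3 days after a move from AZM to placebo go to AZM. OL has no counterpart.

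None of these is an explicit ever/never rule, and assignment at onset is not excluded.

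**3. What per-child assignment would do to events.** Suppose the add-on starts w weeks into the 44, event rates are constant and everyone completes. The share of an AZM-plus child's OL time spent before the add-on is w/44. With one, three or four four-week dose steps this is 4/44 = 9%, 12/44 = 27% or 16/44 = 36%. The same share of that column's events would predate the add-on.

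If a fraction q of children receive an add-on, the share of all events arising on AZM alone that would appear under AZM plus is qw / (qw + 44(1 − q)):
- q = 0.30, w = 4: 1.2/(1.2 + 30.8) = 4%
- q = 0.50, w = 16: 8/(8 + 22) = 27%

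Under assignment at onset the share is 0%. These are event shares. The planned tables count children with an event, so they are only a guide.

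The number of steps is assumed because the titration figure (Protocol Figure 6.b) is not available to me. Protocol 6.1.5 and Protocol Figure 8.a also give different OL starting doses for children of 50 kg or more. Those passages must be reconciled. Either version implies three or four dose levels, inside the range used.

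**4. Two target percentages that answer different questions.** Suppose 200 children are dosed in OL. Of these, 100 never receive an add-on, with 90 at target, and 100 receive one, with 60 at target.
- AZM alone: 90/100 = 90%
- AZM plus: 60/100 = 60%
- Overall: 150/200 = 75%
- At target without add-on, among all dosed: 90/200 = 45%

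If instead 25% or 75% receive an add-on, with the within-column rate held at 90%, the last figure is 0.75 × 90% = 67.5% or 0.25 × 90% = 22.5%.

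**The case against.** The case against is substantial, and most of it limits the point.

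- **Descriptive analysis with an overall column.** SAP 15.3.3.2 plans no model for OL BP, and no text presents the AZM-alone column as a monotherapy control rate. The overall column is free of this selection and reflects the strategy under study, AZM titrated to target with others if needed. This stands, although the overall figure mixes in the add-on effect.
- **Direction.** Children still uncontrolled without an add-on, and early leavers, remain under AZM alone and can lower its rate. Children who stop early for adverse events raise that column's discontinuation rate. The net distortion is therefore not established, and it does not follow that AZM alone must look better tolerated.
- **Certain misattribution of events.** A reader might infer that events on AZM alone will definitely be charged to the combination. The documents do not say so. The table templates that SAP section 8 says accompany the plan are not available here and might settle it.
- **45% as the correct rate.** A reader might take the all-entrants figure as the truth against which 90% is wrong. It is a different, composite measure with its own limits. Protocol 6.1.5 and 6.2.6 allow a lower target in CKD, so a child already below the 90th percentile may receive an add-on and would be scored as not achieving. On down-titration add-ons come off first, so a child may return to AZM alone.
- **Not derivable.** A reader might also infer that the plan's outputs conceal this figure. They do not: the count at target by status and the overall number allow it to be worked out by hand. It is simply not a planned result. Event frequency by regimen cannot be recovered in that way from per-child tables.

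**Conclusion.** The point holds in a limited form. Add-on status is decided after OL entry, largely by failure to reach target on AZM, so the AZM-alone target rate and BP change are response-selected and should not be read as the effect of AZM monotherapy. The size is unknown because the documents give no add-on rate. The 75% to 100% against an assumed 60% shows the mechanism under full follow-up and is not an estimate for this trial.

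For adverse events the finding is an undefined, reversible status. Misattribution follows only on the per-child reading, which is natural but unwritten. Under the stated assumptions it would then move roughly 4% to 27% of AZM-alone events.

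Importance is modest. The OL tables bearing on a secondary safety objective are affected. The primary endpoint and the randomised comparisons are not.

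**What to change.** Amend the SAP and table shells before the final database lock:

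1. **SAP 15.3.3.3.** Make the overall column the main OL result. Add a supplementary descriptive output: the percentage at target at Week 52/Final Visit without add-on, with all children dosed in OL as the denominator. Footnote that children with CKD may receive an add-on in pursuit of a lower target.
2. **SAP 16.1.** Assign OL adverse events by the regimen in use at onset, before or after the add-on date. Give patient-years and exposure-adjusted rates for each regimen. SAP section 13 currently derives exposure by phase only.
3. **SAP section 6.** Define add-on status by date. State how a stopped add-on counts, and whether the stable diuretics permitted in Protocol 7.3.2 count as additional antihypertensives. Label every BP split by add-on status as response-selected. This includes splits by regimen at the visit, because regrouping at each visit does not remove the selection.

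No new data are needed. Add-on dates can come from the open-label concomitant-medication page (SAP section 12), and event start dates are recorded (Protocol 10.2.1.2). The cost is modest programming. The all-entrants figure without add-on will usually look less favourable than the AZM-alone column.

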6.1. REFERENCE START DATE AND STUDY DAY

Reference start date is defined as the day of the first dose of study medication, (Day 1 is the day of the first dose of study medication) and will appear in every listing where an assessment date or event date appears.

Study Day will be calculated from the reference start date and will be used to show start/ stop day of assessments and events.

Study day will be calculated as follows:

- If the date of the event is on or after the reference date, then:
 - Study Day = (date of event reference date) + 1.
- If the date of the event is prior to the reference date, then:
 - Study Day = (date of event reference date).

In the situation where the event date is partial or missing, Study Day, and any corresponding durations will appear partial or missing in the listings.

6.2. **BASELINE**

Unless otherwise specified, baseline is defined as the last non-missing measurement taken prior to reference start date (including unscheduled assessments). In case where the last non-missing measurement and the reference start date coincide, that measurement will be considered pre-treatment.

2014-000674-18 Statistical Analysis Plan Version 7.0 7.0 Document: Version Number: Author: Version Date: 13JAN2020

Template No.: CS_TP_BS016 Revision 5 Reference: CS_WI_BS005

Effective Date: 01Apr2018

7.0

13JAN2020

Version Date:

For subjects randomized but not treated, baseline is defined as the last non-missing measurement taken on or before randomization.

Document: 2014-000674-18 Statistical Analysis Plan Version 7.0 Version Number:

Township No. 00 TD D0046 Davision 5

Template No.: CS_TP_BS016 Revision 5 Reference: CS_WI_BS005

Effective Date: 01Apr2018

Author:

6.3. ENDPOINTS

The primary endpoint for this study is

Change from Week 6/Final Visit of the DB Phase to Week 8/Final Visit of the Withdrawal Phase in trough clinic seDBP between AZM and placebo.

Secondary endpoints for this study are:

- Change from Week 6/Final Visit of the DB Phase to Week 8/ Final Visit of the Withdrawal Phase in trough clinic seDBP and mean arterial pressure (MAP) between AZM and placebo.
- Change from baseline in trough clinic seDBP, seated systolic blood pressure (seSBP), and MAP to Week 6/Final Visit of the DB Phase for AZM and losartan.
- Percentage of subjects who achieve target BP (seDBP, seSBP, both) at Week 8/Final Visit of the Withdrawal Phase, with the target defined as <90th percentile for age, gender, and height.

Safety Endpoints for this study are:

- Adverse events (AEs).
- Physical examination.
- Laboratory tests.
- 12-lead electrocardiogram (ECG) finding.
- Vital signs.
- Anthropometric (height, weight, and body mass index z-scores) measurements.

Additional Endpoints for this study are:

- Change from baseline in trough clinic seDBP, seSBP and MAP at all visits of the DB Phase, excluding the Week 6/Final Visit for AZM and losartan.
- Change from baseline in trough clinic seDBP, seSBP and MAP at all visits of the OL Phase, including Week 52/Final Visit.
- Percentage of subjects who achieve the following additional BP targets (for seSBP, seDBP and both):
- All Subjects:
 - <90th percentile at Week 6/Final Visit of the DB Phase and Week 52/Final Visit of the OL Phase
 - in subjects with chronic kidney disease (CKD).
 - <90th percentile at Weeks 6, 8, and 52/Final Visits of the DB Phase, Withdrawal Phase, and OL Phase, respectively.
 - <50th percentile at Weeks 6, 8, and 52/Final Visits of the DB Phase, Withdrawal Phase, and OL Phase, respectively.
 - Estimation of the exposure using population pharmacokinetics of azilsartan.

Exploratory Endpoints are:

- Change from baseline to Week 6/Final Visit of the DB Phase and to Week 52/Final Visit of the OL Phase in 24-hour, 12-hour, daytime, night time, and trough DBP and SBP by ABPM.
- AZM dose response for change from baseline to Week 6/Final Visit of the DB Phase in clinic seDBP and seSBP.

2014-000674-18 Statistical Analysis Plan Version 7.0 7.0 Document: Version Number: Author: Version Date: 13JAN2020

Template No.: CS_TP_BS016 Revision 5 Reference: CS_WI_BS005

Effective Date: 01Apr2018

RETESTS, UNSCHEDULED VISITS AND EARLY TERMINATION DATA

In general, for by-visit summaries, data recorded at the nominal visit will be presented. Measurements from unscheduled visits will not be included in by-visit summaries but may contribute to the final visit or last observation carried forward (LOCF) value, or best/ worst case value where required.

In the case of a retest (same visit number assigned), the latest available measurement for that visit will be used for by-visit summaries.

Data collected at early termination visits will be mapped to the next planned visit number for that subject. For by-visit summaries, only visits in which a measure was scheduled to be collected will be summarized. Listings will include scheduled, unscheduled, retest and early discontinuation data.

6.5. WINDOWING CONVENTIONS

No visit windowing will be performed for this study.

6.6. SUMMARY STATISTICS

Unless otherwise specified for presentations:

- The default summary statistics for numeric variables are as follows:
 - Number of observations (n).
 - Arithmetic mean.
 - Standard deviation (SD).
 - Minimum (Min).
 - Median.
 - Maximum (Max).
- The default summary statistics for categorical variables are as follows:
 - Number of observations (n).
 - Percentage of subjects with non-missing data per category.

Percentages will be rounded to one decimal place. However, for counts frequencies that are greater than 0, if the calculated percent would round to 0%, then <0.1% will be displayed instead. Likewise, for counts frequencies that are less than the total possible, if the calculated percentage would round to 100%, then >99.9% will be displayed instead. The denominator for each percentage will be the total number of subjects with non-missing data in the treatment group and population (analysis population) being presented, unless otherwise specified.

7.0 Document: 2014-000674-18 Statistical Analysis Plan Version 7.0 Version Number: Author: Version Date: 13JAN2020

Template No.: CS_TP_BS016 Revision 5 Reference: CS_WI_BS005

Effective Date: 01Apr2018

